5.9 Concomitant Medication

5.9.1 General Considerations

The Investigator is to record the use of all concomitant medications, both prescribed and over the counter, in the eCRF. Any medication must have been stopped in the time frame required in the inclusion and exclusion criteria prior to the first dose of study drug. Subjects should be advised against taking any new medication, both prescribed and over the counter, without consulting the investigator, unless the new medication is required for emergency use.

On Day 1, the study site personnel should ensure that subjects continue to meet the inclusion criteria and none of the exclusion criteria (including contraindicated medications). The prohibited and allowed medications with time frames where relevant are summarized below.

5.9.2 Prohibited Medication

- Prior or current use of orlicumab (not a part of this trial).
- Any medical treatment for T2DM started < 90 days prior to study entry.
- Moderate or high-intensity statin use or new use of a low-intensity statin therapy within 90 days of Screening. Low-intensity statin therapy is permitted provided it is limited to lovastatin, fluvastatin, pravastatin ≤ 40 mg daily, simvastatin ≤ 20 mg daily, or pitavastatin ≤ 2 mg daily AND the dose has remained stable and unchanged for ≥ 90 days prior to the screening visit and NO DOSE change is anticipated for the approximate 20-week duration of the trial.
- No use of anti-coagulating agents or anti-thrombotic agents within 90 days prior to the Screening visit. Low dose aspirin limited to ≤ 81 mg daily is permissible provided the dose has remained stable and unchanged for ≥ 90 days prior to the screening visit and NO DOSE change is anticipated for the approximate 20-week duration of the trial. Nonsteroidal anti-inflammatory drugs are not permitted for the duration of the trial from the Screening Visit.
- Antihypertensive medication is permitted provided it is limited to two or less medications and all have been stable and unchanged for ≥ 90 days prior to the screening visit and NO DOSE change is anticipated for the approximate 20-week duration of the trial.
- Paracetamol (acetaminophen) or paracetamol-containing preparations is permitted for pain and fever control but not within 24-hours of a study visit.
- Antihistamines.
- Use of topical therapies, phototherapy (UVA or UVB) or tanning salons for the treatment of psoriasis in the past 4 weeks.
- Use of an IL-23 blocker in the past 180 days, an IL-17 blocker in the past 16 weeks, or a TNF blocker in the past 12 weeks.
- Use of methotrexate, cyclosporine, or apremilast in the past 4 weeks.
- Phosphodiesterase inhibitors (e.g. Viagra, Cialis, Levitra) for at least 72 hours prior to CCTA.
- Metformin for 48 hours after CCTA (day of and day after).

5.9.3 Permitted Medication

Psoriasis rescue medication, (in addition to their current blinded treatment), is limited to topical hydrocortisone 2.5% (cream or ointment) that can be applied twice daily if needed to the face and sensitive intertriginous regions (axilla, groin, breast). Over the counter (non-prescription) applications of coal tar and emollients may be used as necessary.

5.9.4 Rescue Medication

Up to week 15, any subject who, in the opinion of the Investigator, requires medication to treat their psoriasis (in addition to their current blinded treatment) may apply 2.5% hydrocortisone cream or ointment to the face and intertriginous regions (groin, axilla, breast). Over the counter (non-prescription) applications of coal tar and emollients may be used as necessary. The Investigator and qualified staff must direct the administration of this medication and record its use in the concomitant medication section of the source documents and eCRF.

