5.10 General Restrictions

5.10.1 Behavioral Restrictions

Excessive alcohol use or binge drinking will be discouraged during the study, and alcohol will be prohibited 72 hours prior to each visit. Subjects should not use any recreational or illicit drugs within one year prior to Screening through Follow-up Visit. No cannabinoid products will be allowed 1 week prior to each visit.

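### Coal tar and emollients are allowed during treatment with no product-free interval before PASI and sIGA scoring, which may add some noise to percent change in PASI

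*Protocol*

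**What the plan says.** Protocol 5.9.4 (Rescue Medication) permits hydrocortisone 2.5% on the face and skin folds and then adds: "Over the counter (non-prescription) applications of coal tar and emollients may be used as necessary". Section 5.9.3 (Permitted Medication) repeats the permission and says of the hydrocortisone "that can be applied twice daily if needed to the face and sensitive intertriginous regions". For coal tar and emollients neither section limits body site, frequency or timing before a visit.

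On control and recording, 5.9.4 says "The Investigator and qualified staff must direct the administration of this medication" and that they must "record its use in the concomitant medication section of the source documents and eCRF". Section 11.7 names the medical record as the source for start and stop dates of concomitant medications. No section asks for the time of last application.

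Before entry, exclusion 10 in 4.3, repeated in 5.9.2, bars topical psoriasis therapy in the preceding 4 weeks, and 5.9.1 has the exclusions checked again on Day 1.

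The protocol does set pre-visit windows for other substances:
- Alcohol (5.10.1): "alcohol will be prohibited 72 hours prior to each visit".
- Cannabinoids (5.10.1): "No cannabinoid products will be allowed 1 week prior to each visit".
- Paracetamol (5.9.2): it "is permitted for pain and fever control but not within 24-hours of a study visit".
- Phosphodiesterase inhibitors (5.9.2), tied to a single assessment: withheld "for at least 72 hours prior to CCTA".

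**The concern.** PASI is built from erythema, induration and scaling (Protocol 3.1), and scaling is also one of the signs behind the sIGA. A product lying on the skin could plausibly change how scaling looks on the day. If it is present at some scoring visits and absent at others, part of the recorded change reflects scoring conditions and not disease.

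The entry look-back makes this more relevant for coal tar. Coal tar used as treatment should be off the skin at Baseline but is allowed by Week 15, and in that pattern a product effect would not cancel in the change score.

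At stake is precision in percent change in PASI at Week 15, which heads the testing hierarchy (SAP 2.10), in a trial of 75 subjects. The point covers scoring conditions only. It does not concern any treatment effect of coal tar or hydrocortisone used in the preceding weeks.

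**Working it through.** **Text check.** Places where an interval before scoring could stand:

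| Place | Interval without topical product before scoring |
|---|---|
| Protocol 3.1, PASI and IGA descriptions | none |
| Protocol 3.2, visit descriptions | none; the scoring visits ask only for a 10-hour fast |
| Protocol 3.3, Table 1 and footnotes | none |
| Protocol 4.3 exclusion 10, and 5.9.2 | 4 weeks, as an entry look-back |
| Protocol 5.9.3 and 5.9.4 | none |
| SAP 2.6, 2.9 and 2.13 | none, and no rule for rescue or topical use |

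**Inputs for an illustration.** From the documents: PASI region weights 0.1, 0.2, 0.3 and 0.4 (Protocol 3.1); 75 subjects at 2:1, hence 50 and 25; SD 10% and a 7-point difference (SAP 2.11). Assumed, because the documents give neither usage rates nor any product effect: scaling falls by one grade where product is present; Baseline is product-free; all three signs are grade 3 with area score 2 in every region (PASI 9 × 2 = 18, above the entry floor of 12); use is equal in both arms and independent of true response.

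**The SAP's own figure.** Power = Φ(7/(SD × √(1/50 + 1/25)) − 1.96). With SD 10: 7/(10 × 0.2449) = 2.858, and Φ(0.898) = 81.5%, against 80% stated. For 8 points it is 90.4%, against 90% stated. The SAP names no alpha for these figures; two-sided 0.05 is assumed.

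**One grade of scaling.** With equal signs g and a common area score, losing one grade of scaling in regions of total weight w lowers PASI by s = w/(3g) of Baseline. With g = 3:
- legs only: 0.4/9 = 4.44%
- all regions: 1/9 = 11.11%

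**Added variance** = f(1 − f)s², where f is the fraction of subjects affected at Week 15.

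| Case | Added variance | SD | Power |
|---|---|---|---|
| No product effect | 0 | 10 | 81.5% |
| Legs, f = 0.20 | 0.16 × 19.75 = 3.16 | 10.157 | 80.3% |
| Legs, f = 0.10 (half of those users lose a grade) | 0.09 × 19.75 = 1.78 | 10.088 | 80.9% |
| All regions, f = 0.10 | 0.09 × 123.5 = 11.11 | 10.541 | 77.4% |
| All regions, f = 0.05 (half of those users lose a grade) | 0.0475 × 123.5 = 5.86 | 10.289 | 79.3% |

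**If the SAP's SD already contains this noise**, nothing is lost against the planned power. Removing the noise would then raise 81.5% to at most 82.7% (SD √(100 − 3.16) = 9.841, legs case) or 85.8% (SD √(100 − 11.11) = 9.428, all-regions case).

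**Steady use at both visits** largely cancels. With disease unchanged, the sign sum goes from 8 to 8 and the error is 0. With all signs falling from 3 to 2, the true change is (6 − 9)/9 = −33.3%. Product at both visits gives (5 − 8)/8 = −37.5%, an error of 4.2 points. Product at Week 15 only gives (5 − 9)/9 = −44.4%, an error of 11.1 points.

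**Bias** is zero when use is balanced. Each 10 percentage points of imbalance shifts the difference by 0.10 × 4.44 = 0.4 points (legs) to 0.10 × 11.11 = 1.1 points (all regions).

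**The case against.** The strongest reply is that no harm is shown. Nothing in the documents says that coal tar or an emollient lowers a scaling grade, and the power figures rest on assumed use and an assumed effect. The legs case costs 1.2 points of power, and the 4.1-point case needs a full grade lost in all four regions. The SAP describes its SD as on the high side, so the noise may already be covered. All of this stands, and it is why the point is an optional improvement and not an error.

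A second reply is that topicals are already controlled. The 4-week look-back does cover psoriasis topicals before entry, so it would be wrong to say that topicals have no interval at all. Eligibility is also reviewed again before dosing at Visits 2 to 6, and 4.4 lists meeting an exclusion during the study as a reason to discontinue. Read literally, that would conflict with the express permission in 5.9.3 and 5.9.4. It still sets no interval for permitted products, and no eligibility review is listed at Week 15.

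Third, the comparison windows are loose analogies. The documents do not tie the alcohol, cannabinoid or paracetamol windows to skin scoring. They show only that pre-visit windows are a tool this protocol already uses.

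A reader might also infer more than the text supports:
- *That the time of last application is lost for good.* The eCRF is not among the documents; all that can be said is that no section requires the time.
- *That BSA is affected in the same way.* The argument runs through scaling, and BSA is an area percentage.
- *That assessor training is deficient.* Training is mandatory and its content is not given; skin preparation could be covered there.
- *That coal tar is plainly limited to Week 15 and directed by the Investigator.* In 5.9.4 both conditions attach most directly to hydrocortisone, and 5.9.3 repeats the coal tar permission without either.

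**Conclusion.** The gap is real: during treatment the plan sets no product-free interval before PASI and sIGA, so scaling may be scored with product on the skin at some visits and not at others. The likely consequence is modest extra noise in percent change in PASI. Under the stated assumptions it is worth about 1 to 4 points of power; its true size is unknown and may be zero. Any effect on sIGA success is probably small, because success also depends on colour and on absence of thickening.

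A reader might infer that this could produce a false-positive result. The documents do not support that: treatment is double-blind, nothing suggests heavier use on orticumab, and balanced use gives no bias. Heavier use on placebo would shrink the difference, which is conservative.

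This is worth considering, with medium confidence, because the remedy is cheap and nothing in the plan would let an analysis adjust for differing scoring conditions.

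**What to change.** Leave access to the products unchanged.

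1. In 5.9.3 and 5.9.4, state that no topical product, plain emollient included, is applied within 24 hours before PASI and sIGA scoring at Day 1 and Weeks 1, 3, 7, 11 and 15. The minimum would be none on the day of the visit until scoring is done. The 24 hours is borrowed from the paracetamol rule; the documents give no product-specific basis for it.
2. Add the rule to the instructions that eligible subjects receive at Screening (3.2.1.1). It then starts after consent, and nobody is asked to withhold product before the Screening scores.
3. Record date and time of last application on the efficacy eCRF page.
4. If the interval is missed, score anyway, record the time and keep the subject in the analysis. Those scores stay unstandardised, but the field shows how often this happens.

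Cost: one sentence in each of the two sections, one line of subject instruction and one eCRF field. The burden on subjects is up to 24 hours without product before six visits. The rule standardises scoring conditions only and does not remove any treatment effect of products used earlier.

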5.10 General Restrictions

5.10.1 Behavioral Restrictions

Excessive alcohol use or binge drinking will be discouraged during the study, and alcohol will be prohibited 72 hours prior to each visit. Subjects should not use any recreational or illicit drugs within one year prior to Screening through Follow-up Visit. No cannabinoid products will be allowed 1 week prior to each visit.

5.10.2 Contraceptive Measures

The subject or their heterosexual partner (if applicable) should be surgically sterile (vasectomy, hysterectomy, bilateral tubal ligation [both tubes tied], or bilateral oophorectomy [both ovaries removed]). If not, and the female subject or partner is of childbearing potential (could become pregnant), the subject must agree to use highly effective contraception during heterosexual intercourse throughout the study period and for 90 days following last dose of study drug. Examples of a highly effective method of contraception include double barrier methods (e.g., use of a condom and spermicide along with [choose 1 of the following] a diaphragm; hormone-containing pill, injection or implant; or intrauterine device [IUD]). The male subject must not donate sperm while participating in this study and for 90 days after receiving the last dose of study drug.

6 STUDY PROCEDURES AND ASSESSMENTS

6.1 PHARMACOKINETIC EVALUATIONS

Blood samples will be collected at the time points indicated in [Table 1](#). The concentration of orticumab in these samples will be analyzed by a contract bioanalytical laboratory. Aliquots of plasma samples from each time point will be stored frozen for potential future evaluation of additional biomarkers for preliminary information only. Full details of the methodology will be presented in the bioanalytical report, which will be appended to the clinical study report.

6.2 PHARMACOKINETIC SAMPLING

Samples of venous blood will be obtained in 10 mL K2EDTA tubes (a minimum of 8 mL per time point required) just prior to dose administration at the time points indicated in [Table 1](#). The K2EDTA tubes and associated labels will be provided by the sponsor or their designee.

Immediately after collection, the tube will be gently inverted several times to mix the anticoagulant with the blood sample. The plasma fraction will be separated by placing the collection tube into a refrigerated centrifuge (4°C to 8°C) for 10 minutes at approximately 1500 × g. The plasma fraction will be withdrawn by pipette and divided into 2 polypropylene freezing tubes (with each tube receiving approximately equal aliquots). All sample collection and freezing tubes will be clearly labeled in a fashion that identifies the subject, the study period, and the collection time. Labels will be fixed to freezing tubes in a manner that will prevent the label from detaching after freezing. All plasma samples will be processed and placed into a freezer (-70°C) within 1 hour after collection.

All plasma samples will be stored frozen (-70°C) until they are shipped to the bioanalytical facility. Prior to shipping, the samples will be packed into thermal insulated containers (provided by Sponsor or their designee) and packed in sufficient dry ice to assure that they remain frozen for a minimum of 72 hours and protected from breakage during shipment. The bioanalytical facility will be notified of the shipment via e-mail or facsimile. Samples will be shipped by overnight priority courier. The samples will be divided into 2 shipments, each containing 1 aliquot of plasma for each time point. After receipt of verification that the first shipment was received by the analytical facility, the second shipment will be sent.

All samples will be shipped to: PPD Labs Inc., Global Central Laboratories, [name].

6.3 SAFETY EVALUATIONS

6.3.1 Adverse Events

The investigator will determine during the course of all study periods whether any AEs have occurred. The subjects will be questioned in a general way and no specific symptoms will be suggested. [Section 7](#) contains additional information with regard to AEs.

6.3.2 Clinical Laboratory Tests

Blood for clinical safety laboratory assessments will be collected and processed using standard procedures as indicated in [Table 1](#). Clinical laboratory tests will be performed by a central laboratory designated by the Sponsor.

The Principal Investigator will review all laboratory results and initial and date a copy for storage in the source document. A clinically significant abnormal lab test will be reported as an AE. In the event of abnormal clinical laboratory values, the Investigator will make a judgment whether the abnormality is clinically significant.

A procedures manual for Screening and safety clinical laboratory sample collection, handling, and shipment to the central laboratory will be provided to each study site by Sponsor or Sponsor designee prior to the start of the study.

Laboratory reports received from the central laboratory should be reviewed, signed, and dated by the investigator or delegated physician. Each abnormal result will be assessed as clinically or not clinically significant and a comment will be provided for all out-of-range analytes deemed clinically significant (i.e., document probable cause for abnormal results). Laboratory data will be collected electronically by Sponsor or their designee and transferred to the contract research organization (CRO) handling the eCRF form data for integration with the eCRF data.

6.3.2.1 Clinical Safety Labs

The following clinical safety labs will be performed:

Hematology: Hematocrit, hemoglobin, red blood cell (RBC) count, white blood cell (WBC) count, differentials (neutrophils, eosinophils, basophils, lymphocytes, and monocytes), platelet count, and reticulocytes.

Chemistry: Albumin, alkaline phosphatase, alanine aminotransferase (ALT), aspartate aminotransferase (AST), blood urea nitrogen (BUN), calcium, chloride, CO₂, creatinine, direct bilirubin, gamma-glutamyl-transferase (GGT), glucose, lactate dehydrogenase (LDH), phosphorus, potassium, sodium, total bilirubin, total cholesterol, total protein, uric acid, standard lipid panel (Total Cholesterol, triglycerides, LDL-cholesterol and HDL-cholesterol).

6.3.2.2 Coagulation Parameters

An activated partial thromboplastin time (aPTT) test will be performed at Screening, Visits 1, 4, 7 and any unscheduled visit (if applicable) as indicated in ([Table 1](#)).

6.3.2.3 Pregnancy Test

For females, a serum pregnancy test will be performed at Screening and a urine pregnancy test at Visits 1 (Baseline), 4, 5, 6, 7, and 8 (post-treatment Follow-up Visit) as indicated in ([Table 1](#)).

6.3.2.4 Immunogenicity Testing

Immunogenicity will be assessed at Baseline (Day 1, prior to dosing), at Visit 4 (Week 3, prior to dosing), and at Visit 7 (Week 15) as indicated in ([Table 1](#)).

6.3.2.5 Additional Screening Bloodwork

In addition to the blood tests listed above serology (Hepatitis B and C, and HIV) will be performed at Screening ([Table 1](#)).

6.3.3 Vital Signs

Vital signs (blood pressure [BP] [mmHg] and heart rate [bpm]) will be measured at the clinic visits or time points indicated in [Table 1](#). BP will be measured after at least a 5-minute rest in the sitting position. BP will be measured with a standard mercury sphygmomanometer. Whenever possible, the measurements should be made by the same personnel using the same device at each evaluation.

6.3.4 Physical Examination

A physical examination will be performed at the time points indicated in [Table 1](#). This evaluation will include examination of the following body systems: general appearance; eyes; ears, nose, and throat; head and neck; chest and lungs; cardiovascular; abdomen; musculoskeletal; lymphatic; dermatological; neurological; and extremities. Urogenital and psychiatric abnormalities will be accessed as part of the subject's medical history at Screening and any abnormalities (i.e., if the subject has a complaint for that system) in these systems during the treatment period will be recorded as AEs.

6.3.5 Height and Weight

Height and weight will be measured at Screening and weight will be measured at Weeks 0, 3, 7, 11, 15, and UNS Visit ([Table 1](#)).

6.3.6 Demographics and Medical History and Prior Medications

At Screening, demographics (sex, DOB, race, and ethnicity) and a brief medical history (including tobacco and alcohol use) will be collected by subject interview. Medications and supplements, recent blood donations, illnesses, and participation in other Investigational Drug trials or clinical trials will also be recorded.

6.4 Total Blood Volume

The total volume of blood obtained from an individual study participant is expected to be approximately 164 mL, including PK samples and clinical laboratory tests.

Table 2: Blood Draw Volumes

| Assay | Volume per Sample (mL) | Total Number of Samples | Total Volume (mL) |
|------------------------------------------------------------------------------------------------------------|------------------------|-------------------------|-------------------|
| Serum Pregnancy | 4 mL | 1 | 4 mL |
| Immunogenicity | 4 mL | 3 | 12 mL |
| PK | 4 mL | 6 | 24 mL |
| Hematology | 4 mL | 4 | 16 mL |
| Serum Chemistry [^] | 8 mL | 5 | 40 mL |
| aPTT | 3 mL | 4 | 12 mL |
| Biomarkers | 8 mL | 7 | 56 mL |
| Total blood volume (entire study) | | | 164 mL |
| [^] Serum chemistry will include serology (Hepatitis B and C, and HIV) and a standard lipid panel | | | |

6.5 Efficacy Assessments

6.5.1 Psoriasis Measures

Mean percent change from Baseline in PASI at Weeks 1, 3, 7, 11, and 15, compared to placebo.

Percentage of Participants achieving PASI75 and PASI50 from Baseline at Weeks 1, 3, 7, and 11, compared to placebo.

Percentage of participants achieving treatment success (clear =0 or almost clear =1) and greater than or equal to (\geq) 2 Point Improvement at Weeks 1, 3, 7, 11, and 15 on the 5-point static Investigator's Global Assessment modified 2011 version (sIGA).

Mean percent change from Baseline in BSA at Weeks 1, 3, 7, 11, and 15, compared to placebo.

Mean percent change from Baseline in DLQ1 at Weeks 1, 3, 7, 11, and 15, compared to placebo.

Mean change from Baseline in Itch Numerical Rating Scale Score at Weeks 3 and 15, compared to placebo.

6.5.2 Cardiometabolic and Inflammatory Biomarkers

Mean change from Baseline in cardiometabolic and inflammatory biomarkers at Weeks 3 and 15 in:

- Blood serum lipid parameters
 - ApoB, Apo A1, VLDL-c, oxLDL, oxHDL, Lp(a), oxLp(a), NMR-LP-4
- Blood serum inflammation biomarkers
 - Interleukin-6 (IL-6), IL-1 β , IL-17, tumor necrosis factor-alpha (TNF- α), osteoprotegerin, high-sensitivity C-reactive protein (hs-CRP), serum amyloid A (SAA), and monocyte chemoattractant protein-1 (MCP-1)
- Blood serum HDL efflux efficiency
 - ABCA-1

